For all participants, hypothalamic-pituitary-adrenal axis integrity will be evaluated when they have been on 5 mg/day for 4 weeks and prior to any further tapering down the OCS dose (for participants with baseline OCS doses equal to 5 mg/day, this will be assessed 4 weeks after the first dose of tezepelumab administration and before initiation of the OCS reduction phase). A screening method with morning serum cortisol will be done (8 to 9 am morning cortisol level) for all participants, to determinate whether the participants have normal cortisol levels, complete AI, or indeterminate results. Participants with normal morning cortisol levels will continue down-titration. Participants with complete AI will delay titration and repeat the test 3 months later. For participants showing indeterminate results, an ACTH stimulation test will be performed and decisions regarding how to continue OCS down-titration will be based on results of this test (see Table B).

Table B Adrenocorticotropic Hormone Stimulation Testing

	A	CTH stimulation test resul	lts
	Normal (> 450 nmol/L ^a)	Partial AI (250-450 nmol/L ^b)	Complete AI (< 250 nmol/L°)
OCS down-titration	Reduction of 2.5 mg Q4W	Reduction of 1 mg Q4W	Continue on same OCS dose
Repeat morning cortisol test for further OCS down-titration	No need	2 months later	3 months later

Abbreviations: OCS = oral corticosteroids; Q2W = every two weeks; Q4W = every four weeks.

- a. > 675 nmol/L for participants taking oestrogen-containing contraceptives
- b. 375-675 nmol/L for participants taking oestrogen-containing contraceptives
- c. < 375 nmol/L for participants taking oestrogen-containing contraceptives

For sites where no tetracosactide is available/registered, an alternative method to identify AI is provided (see Appendix M).

In addition to a participant's asthma symptoms, investigators will use the participant's weekly ACQ-6 scores (completed by the participant at home by means of a handheld electronic participant-reported outcome device), and will further reduce the OCS dose unless asthma control is lost (deterioration or exacerbation as described below) or AI prevents further dose reduction.

Asthma deterioration will be defined by an increase of ACQ-6 score \geq 0.5 from baseline. Asthma exacerbation will be defined by worsening of asthma symptoms that leads to:

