- Cortisol levels are indeterminate (Table 9): participant will be instructed to maintain the current OCS dose and will undergo the ACTH stimulation testing (or alternative method, see Appendix M). Decisions regarding how to continue

OCS down-titration will be based on the results of the ACTH stimulation testing (or alternative method, see Appendix M).

• If complete AI is confirmed (Table 9): participant will be instructed to maintain the current OCS dose until there is evidence of recovery from the complete AI without worsening of asthma control. The morning cortisol test will be repeated 3 months later.

If the morning cortisol is in the indeterminate range, the ACTH stimulation test will be done within approximately 1 week (see Section 8.2.1.2 for details). The ACTH stimulation test (Table 10) can determine whether the participant has:

- Normal cortisol levels
- Complete AI
- Partial AI

Decisions regarding how to continue OCS down-titration will be based on results of this test (Table 3).

Table 3 OCS Down-titration Scheme Using ACTH Stimulation Test

	Normal (> 450 nmol/L ^a)	Partial AI (250-450 nmol/L ^b)	Complete AI (< 250 nmol/L°)
OCS down-titration	Reduction of 2.5 mg Q4W	Reduction of 1 mg Q4W	Continue on same OCS dose
Repeat morning cortisol test for further OCS down-titration	No need	2 months later	3 months later

Abbreviations: ACTH = adrenocorticotropic hormone; OCS = oral corticosteroids; Q2W = every two weeks; Q4W = every four weeks.

- 2 > 675 nmol/L for participants taking oestrogen-containing contraceptives
- b. 375-675 nmol/L for participants taking oestrogen-containing contraceptives
- c. < 375 nmol/L for participants taking oestrogen-containing contraceptives

For sites where tetracosactide is not available or not registered, an alternative method to identify AI is provided (see Appendix M).

At each visit, in addition to the participant's asthma symptoms, investigators will use the participant's weekly ACQ-6 scores (completed by the participant at home by means of a handheld electronic participant-reported outcome device [ePRO]), and will further reduce the OCS dose unless asthma control is lost (deterioration or exacerbation as described below) or AI prevents further dose reduction.

Asthma deterioration will be defined by an increase of ACQ-6 score \geq 0.5 from baseline. Asthma exacerbation will be defined by worsening of asthma symptoms that leads:

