8.2.1 Hypothalamic-pituitary-adrenal Axis Evaluation

For all participants, HPA axis integrity will be evaluated after 4 weeks on 5 mg/day and prior to tapering down the OCS dose (for participants with baseline OCS doses equal to 5 mg/day, this will be assessed 4 weeks after the first dose of tezepelumab administration and before initiation of the OCS reduction phase).

First, a screening method with morning serum cortisol is done (8-9 am morning cortisol level), to evaluate whether the participant has:

- Normal cortisol levels (Table 9)
- Complete AI (Table 9).

Cortisol levels from the morning cortisol test that are below normal range and above the complete AI range are considered 'indeterminate' (Table 9), and require additional testing described below (for sites where tetracosactide is not available or not registered, please see Appendix M).

If the morning cortisol is in the indeterminate range, then the ACTH stimulation test is done within approximately 1 week (see Section 8.2.1.2 for details). The ACTH stimulation test is more specific than the morning cortisol test, and can determine whether the participant has:

- Normal cortisol levels: > 450 nmol/L (> 675 nmol/L for participants taking oestrogen-containing contraceptives)
- Complete AI: < 250 nmol/L (< 375 nmol/L for participants taking oestrogen-containing contraceptives)
- Partial AI: 250 to 450 nmol/L (375 to 675 nmol/L for participants taking oestrogen-containing contraceptives).

For morning serum cortisol and ACTH stimulation tests, hold OCS dose and other concomitant medications that could interfere with cortisol results as follows (see Section 6.5):

- The last OCS dose should be taken \geq 24 hours prior to testing
- Participants must not take ICS (or ICS/LABA if in single inhaler) treatment on the
 morning of the morning cortisol level/ACTH stimulation test (for participants taking a
 once-daily ICS/LABA formulation, eg, fluticasone furoate/vilanterol, participants must
 not take the treatment ≤ 24 hours prior to the morning of the morning cortisol
 level/ACTH stimulation test)
- If a participant requires a short course of macrolides, antivirals, or azoles, there must be a window of ≥ 1 week prior to the testing of cortisol levels.

The process will be as described in Figure 3.

[figure not shown]

Figure 3 Hypothalamic-pituitary-adrenal Axis Evaluation

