8.2.1.1 Morning Cortisol Test

The morning cortisol test will be done in all participants 4 weeks after reaching the 5 mg dose of OCS, and before further dose reductions. It is also done 3 months after a participant has completed a test indicating complete AI.

Serum samples for cortisol will be collected between 8 and 9 am and will be sent to a central laboratory for evaluation.

The following values will be used to define AI status for the morning cortisol test:

Table 9 Cortisol Status

AI status	SI units	Participants taking oestrogen- containing contraceptives
Normal	>350 nmol/L	>700 nmol/L
Indeterminate results	100 - 350 nmol/L	200 - 700 nmol/L
Complete AI	<100 nmol/L	<200 nmol/L

Once the results are available, the site will inform the participant of the results via telephone. For sites where tetracosactides are available, and depending on the result, the actions that will be implemented are as follows:

- If cortisol levels are within normal range and the participant does not exhibit any signs and/or symptoms of AI, the participant will continue OCS down-titration by 2.5 mg Q4W
- If cortisol levels are within normal range but the participant exhibits signs and/or symptoms of AI, then OCS down-titration should continue at a slower pace (1 mg Q4W).
- If cortisol levels are below the normal range and above the complete AI range (indeterminate result), then the participant will be instructed to maintain the current OCS dose and come back to the site within 1 week for an ACTH stimulation test (Section 8.2.1.2)
- If complete AI is confirmed, sites will inform participant that the OCS dose will remain the same without further reduction until there is evidence of recovery from the complete AI without worsening of asthma control. The morning cortisol test and associated clinical assessments (see Table 1) will be repeated 3 months later. After the repeat morning cortisol test, the site will inform the participant based on the results as follows:
 - If morning cortisol results indicate normal cortisol values, then reductions will be 2.5 mg Q4W, and the participant would subsequently move to maintenance at the OCS lowest possible dose
 - If morning cortisol results are indeterminate, then reductions will be delayed further, and the participant would return approximately 1 week later for an ACTH stimulation test:
 - o If normal result after ACTH stimulation (Table 10): reduce by 2.5 mg Q4W then move to maintenance at the lowest possible dose

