Appendix M Alternative Method for Hypothalamic-pituitary-adrenal Axis Evaluation

FOR USE ONLY IF TETRACOSACTIDE IS NOT REGISTERED IN YOUR COUNTRY OR WITH PERMISSION FROM LABCORP IF TETRACOSACTIDE IS NOT AVAILABLE AT YOUR SITE

First test (before reducing the maintenance OCS dose below 5 mg per day)

Sample	8–9am cortisol cortisol ^a	Action	Status
1	>350 nmol/L	Continue down-titration (2.5 mg every 4 weeks to zero)	No AI
	100–350 nmol/L	Repeat 8–9am cortisol approximately 1 week later (instead of performing ACTH stimulation test) and interpret according to sample 2 below	Indeterminate
	<100 nmol/L	Delay titration and repeat test in 3 months ^b	Complete AI

Second test - Approximately 1 week after the first test in case the first test was indeterminate

Sample	8–9am cortisol cortisol ^a	Action	Status
2	>350 nmol/L	continue down-titration (2.5 mg every 4 weeks to zero)	No AI
	≤350 nmol/L or when signs or symptoms of AI are present	If serum cortisol ≥250 nmol/L on either sample 1 or sample 2, proceed with slow titration (1 mg every 4 weeks) until the participant reaches a prednisolone / prednisone dosage of 3 mg per day and then repeat testing ^b (ie, at 2 months – see 3 rd test below)	Partial AI
		If serum cortisol <250 nmol/L on both samples 1 and 2, delay titration and repeat test in 3 months ^b (see 3 rd test below)	Complete AI

Third test - 2 or 3 months later (see Section 8.2.1)

[figure not shown]
Sample	8–9am cortisol	Action	Status
	cortisol ^a		
3	>350 nmol/L	Continue down-titration (2.5 mg every 4 weeks to zero)	No AI
	100–350 nmol/L	Repeat 8–9am cortisol approximately 1 week later and interpret according to sample 4 below	Indeterminate
	<100 nmol/L	Delay titration and repeat test in 3 months ^b	Complete AI

Fourth test - Approximately one week after the third

Sample	8–9am cortisol cortisol ^a	Action	Status
4	>350 nmol/L	Continue down-titration (2.5 mg every 4 weeks, or 1 mg every 4 weeks if signs or symptoms of AI are present)	No AI
	≤350 nmol/L or when signs or symptoms of AI are present	If serum cortisol ≥250 nmol/L on either sample 3 or sample 4, continue with slow titration (1 mg every 4 weeks) until the participant reaches a prednisolone / prednisone dosage of 1 mg per day and then repeat testing (ie, at 2 months) and discuss with endocrinologist ^b	Partial AI
		If serum cortisol <250 nmol/L on both samples 3 and 4, delay titration and discuss with endocrinologist	Complete AI

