^a NB thresholds must be adjusted upward for women receiving oral oestrogen therapy as per existing protocol.

^b Participants will be educated for symptom awareness of adrenal suppression and use of steroid emergency cards.

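### Appendix M raises cortisol cut-offs for women on oral oestrogen, the rest of the protocol only for contraceptive users, and Appendix M's 250 nmol/L split has no stated raised value

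*Protocol*

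**What the plan says.** Protocol Section 8.2.1.1 has every participant take an 8–9 am serum cortisol after 4 weeks on 5 mg/day. Table 9 classifies it with one standard column and one raised column, the latter headed "Participants taking oestrogen- containing contraceptives". The ACTH stimulation cut-offs are raised for the same group in Section 8.2.1 ("Normal cortisol levels: > 450 nmol/L (> 675 nmol/L for participants taking oestrogen-containing contraceptives"), in Synopsis Table B ("> 675 nmol/L for participants taking oestrogen-containing contraceptives"), in Section 4.1 Table 3 ("375-675 nmol/L for participants taking oestrogen-containing contraceptives") and in Table 10.

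Appendix M replaces the ACTH test with repeat morning cortisols. It is headed "FOR USE ONLY IF TETRACOSACTIDE IS NOT REGISTERED IN YOUR COUNTRY", with a second route, by permission, for sites that cannot obtain the product. Its first and third tests use Table 9's standard cut-offs of 350 and 100 nmol/L. Its second and fourth tests add a basal split at 250 nmol/L; for example, "If serum cortisol <250 nmol/L on both samples 1 and 2" means complete adrenal insufficiency (AI) and a hold. Footnote a then states that "thresholds must be adjusted upward for women receiving oral oestrogen therapy as per existing protocol". Appendix M prints no raised figures.

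SAP Section 4.2.1.7 records ACTH testing as unavailable in Poland, Bulgaria and Latvia, and makes access to the test a subgroup for the primary endpoints.

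**The concern.** The same blood test with the same standard cut-offs appears in two places, and the two places name different women for the upward adjustment. Non-contraceptive oral oestrogen is named only in Appendix M. By the footnote's own logic, a woman taking it needs higher cut-offs, yet Table 9 gives her the standard ones at a site that has the ACTH test. If her reading is normal there, she goes below 5 mg/day without a confirmatory test. She also misses the steroid-card education in Section 8.2.1.3, which is tied to partial or complete AI.

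Separately, the footnote makes the upward adjustment mandatory, but a site cannot work out from the protocol what the basal 250 becomes. That number decides between a slow taper and a hold.

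**Working it through.** **Inputs (nmol/L)**

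| Source | Cut-off | Standard | Raised | Raised / standard |
|---|---|---|---|---|
| Table 9, morning cortisol | normal above | 350 | 700 | 700/350 = 2 |
| Table 9, morning cortisol | complete AI below | 100 | 200 | 200/100 = 2 |
| Table 10, ACTH-stimulated peak | normal above | 450 | 675 | 675/450 = 1.5 |
| Table 10, ACTH-stimulated peak | complete AI below | 250 | 375 | 375/250 = 1.5 |
| Appendix M tests 1 and 3 | as Table 9 | 350 and 100 | by reference back | – |
| Appendix M tests 2 and 4 | partial / complete split | 250 (basal) | not stated | – |

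**Step 1: the trigger.** Take a woman on non-contraceptive oral oestrogen, morning cortisol 400, no signs of AI.

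- ACTH site: she is not a contraceptive user, so the standard column applies. 400 > 350 is normal. The action under "If cortisol levels are within normal range and the participant does not exhibit any signs and/or symptoms of AI" is 2.5 mg every 4 weeks, with no further test.
- Appendix M, footnote read literally, with Table 9's raised figures: 200 ≤ 400 ≤ 700 is indeterminate. She repeats the test about a week later.

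The two routes disagree for every reading of 351–700 (normal versus indeterminate) and of 100–199 (indeterminate versus complete AI).

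**Step 2: can such a woman be enrolled?** Neither Section 5.2 nor Table 6 excludes oestrogen. Criterion 7 admits permanently sterilised women with no hormone condition. Its non-hormonal contraceptive options, such as tubal occlusion or a vasectomised partner, do not bar separate oestrogen. The postmenopausal definitions largely close that route, because exogenous hormones must have stopped. The documents give no count.

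**Step 3: the basal 250 split.** Let M be the higher of the two samples, with sample 1 in the raised indeterminate band (200–700) and sample 2 at or below 700. For a raised cut-off c, the result is partial AI if M ≥ c and complete AI if M < c. The candidates are:

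- c = 250 × 1.5 = 375, the printed ACTH-test figure;
- c = 250 × 2 = 500, Table 9's basal factor.

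The class changes exactly when 375 ≤ M < 500, that is M = 375–499.

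| Samples | c = 375 | c = 500 |
|---|---|---|
| 300, 300 | complete | complete |
| 400, 400 | partial: 1 mg every 4 weeks | complete: hold, retest at 3 months |
| 500, 500 | partial | partial |

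**Step 4: what a change of class costs in time.** From the first permitted step at 5 mg:

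- 2.5 mg steps (5, 2.5, 0) are two steps 4 weeks apart: (2 − 1) × 4 = 4 weeks to zero.
- 1 mg steps (5, 4, 3, 2, 1, 0) are five steps: (5 − 1) × 4 = 16 weeks if the pace never changes. The 2-month retest may change it.
- Complete AI adds a 3-month hold before any step.

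**The case against.** The best defence starts from Section 8.2.1.1. It gives Table 9 as the classification for a test done in all participants, and only afterwards narrows to sites with tetracosactide, for the actions rather than the cut-offs. The footnote also refers back to the existing protocol. So the raised 700 and 200 already reach Appendix M sites. That stands. A reader might infer that those sites have no raised figures at all, or that women on intravaginal or transdermal combined contraceptives (allowed by criterion 7) lose the adjustment there. The documents do not support either inference, because Table 9 covers those women at every site.

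The body contains only one oestrogen adjustment, for contraceptives, so the footnote may simply be shorthand for it. This is plausible and lowers confidence, but the footnote does not say so and its words describe a different group.

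A reader might also infer a strict split by country from the SAP. That goes too far: sites elsewhere may use Appendix M with permission, and the documents do not say how many participants each route will cover. The SAP's ACTH-access subgroup will show results by availability of the test, although that does nothing for an individual woman's taper.

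Finally, 500 is tempting for the basal 250 because it follows Table 9's factor. The only raised 250 in print is 375, and Appendix M's second sample stands in for the ACTH test to which 375 belongs. Arithmetic cannot choose between them.

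**Conclusion.** Two things hold. The trigger for raised cut-offs differs between the body and Appendix M footnote a. Read literally, this classes a woman on non-contraceptive oral oestrogen differently at 351–700 nmol/L according to the testing route. And the basal 250 split has no stated raised value, with the action depending on the choice when the higher sample is 375–499 nmol/L. The second gap does not depend on how the trigger is read.

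The point is minor, with moderate confidence. It assumes that the footnote means what it says and that Table 9's raised figures are the ones it refers to. The number of women affected is not given and is probably small. It would be wrong to infer material damage to the primary results. Testing starts only once 5 mg/day is reached, so the endpoint of 5 mg or less is largely untouched, and the effect on complete discontinuation is confined to these women. Symptoms of AI slow the taper even after a normal result.

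**What to change.** - Use one trigger in Tables B, 3, 9 and 10, Section 8.2.1 and Appendix M: oestrogen-containing contraceptives by any allowed route, or oral oestrogen therapy. If the sponsor intended contraceptives only, footnote a should use the body's term.
- In Appendix M, refer explicitly to Table 9's 700 and 200 as the raised values for 350 and 100.
- Have the endocrinologists on the Scientific Committee (Appendix A 5) set one raised value for the basal 250 cut-off, without presuming 500, and print it for tests 2 and 4.

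This changes protocol wording only; the SAP needs no change. The cost is an occasional extra test or a slower taper for a few women.

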Appendix N Abbreviations

Abbreviation or special term	Explanation
AAER	Annualised asthma exacerbation rate
ACQ-6	Asthma Control Questionnaire 6
АСТН	Adrenocorticotropic hormone
AD	Atopic dermatitis
ADE	Adverse device effect
AE	Adverse event
AESI	Adverse event of special interest
AI	Adrenal insufficiency
AIRQ	Asthma Impairment and Risk Questionnaire
ALP	Alkaline phosphatase
ALT	Alanine aminotransferase
APFS	Accessorised pre-filled syringe
AQLQ(s)+12	Standardised Asthma Quality of Life Questionnaire for 12 years and older
AST	Aspartate aminotransferase
ATS/ERS	American Thoracic Society/European Respiratory Society
BD	Bronchodilator
BP	Blood pressure
CFR	Code of Federal Regulations
CI	Confidence interval
COVID-19	Coronavirus disease 2019
CRO	Contract research organisation
CSP	Clinical Study Protocol
CSR	Clinical Study Report
DAE	Discontinuation of investigational product due to adverse event
DBL	Database lock
DILI	Drug Induced Liver Injury
DMP	Data Management Plan
eCRF	Electronic case report form
EDC	Electronic data capture
EOS	Eosinophil
ЕОТ	End of Treatment
ePRO	Electronic patient-reported outcome device
ER	Emergency room

Abbreviation or special term	Explanation
FAS	Full analysis set
FeNO	Fractional exhaled nitric oxide
FEV_1	Forced expiratory volume in 1 second
GC	Glucocorticoid
GCP	Good Clinical Practice
HCG	Human chorionic gonadotropin
НСР	Health Care Professional
HL	Hy's Law
HPA	Hypothalamic-pituitary-adrenal
IATA	International Airline Transportation Association
IB	Investigator brochure
ICH	International Conference on Harmonisation
ICF	Informed Consent Form
ICS	Inhaled corticosteroids
IEC	Independent Ethics Committee
IgE	Immunoglobulin E
FEIA	Fluorescent enzyme immunoassay
IgG2λ mAb	Fully human immunoglobulin 2λ monoclonal antibody
IL-	Interleukin-
IM	Intramuscular
IMP	Investigational Medicinal Product
IP	Investigational product
IPD	Premature investigational product discontinuation
IRB	Institutional Review Board
ISF	Investigator Study File
IxRS	Interactive (voice or web) response system
IV	Intravenous
LABA	Long-acting β ₂ agonist
LAMA	Long-lasting muscarinic antagonist
LRTI	Lower respiratory tract infection
LTRA	Leukotriene receptor antagonist
MCID	Minimal clinically meaningful difference
MedDRA	Medical Dictionary for Regulatory Activities
OCS	Oral corticosteroids

Abbreviation or special term	Explanation
PHL	Potential Hy's Law
PI	Principal investigator
PRO	Patient-reported outcome
PT	Preferred term
Q2W	Every 2 weeks
Q4W	Every 4 weeks
SABA	Short-acting β-agonist
SADE	Serious adverse device effect
SAE	Serious adverse event
SAP	Statistical Analysis Plan
SARS-CoV-2	Severe acute respiratory syndrome coronavirus 2
SC	Subcutaneous
SGRQ	St. George's Respiratory Questionnaire
SoA	Schedule of Activities
SOC	System organ class
SOP	Standard Operating Procedures
TBL	Total bilirubin
TSLP	Thymic stromal lymphopoietin
TSLPR	Thymic stromal lymphopoietin receptor
ULN	Upper limit of normal
URTI	Upper respiratory tract infection
USADE	Unanticipated serious adverse device effect
WHO	World Health Organization
WOCBP	Women of childbearing potential

FEV ₁	Forced Expiratory Volume in 1 second
GAM	Generalized Additive Model
HCG	Human Chorionic Gonadotropin
HL	Hy's Law
IA	Interim Analysis
IgE	Immunoglobulin E
IMP	Investigational Medicinal Product

IP	Investigational Product
IPD	Investigational Product Discontinuation
LABA	Long-acting β ₂ agonist
LOESS	Locally Estimated Scatterplot Smoothing
MedDRA	Medical Dictionary for Regulatory Activities
MICD	Minimal Clinically Important Difference
NA	Not Applicable
OCS	Oral Corticosteroids
PHL	Potential Hy's Law
PD	Protocol Deviation
PI	Principal Investigator
PK	Pharmacokinetics
SAE	Serious Adverse Event
SAP	Statistical Analysis Plan
SGRQ	St. George's Respiratory Questionnaire
SoA	Schedule of Activities
ULN	Upper Limit of Normal
WHO	World Health Organization

AMENDMENT HISTORY

CATEGORY Change refers to:	Date	Description of change	In line with CSP?	Rationale
N/A	10-Mar-2022	Initial approved SAP	N/A	N/A
Derivation of primary or secondary endpoints	11-Apr-2022	Lower visit window (Section 3.3.2) used for OCS dose derivation at Week 52 updated from "Visit 15 date + 2 days" to "Visit 14 + 2 days".	N/A	To provide correct information of the derivation.
Derivation of primary or secondary endpoints	11-Apr-2022	Clarification added that if the end date of the first exacerbation and the start date of the second exacerbation are less than 7 days, then it is counted as one exacerbation (Section 4.2.2.2).	Yes, CSP v2.0	To clarify rules of counting the number of exacerbations.
Derivation of primary or secondary endpoints	1-Dec-2022	Composite strategy updated to hypothetical strategy for handling intercurrent event of therapy initiation with another biologic for treatment of asthma (Section 1.1).	Yes, CSP v3.0	To correct the name of the strategy.
Derivation of primary or secondary endpoints	1-Dec-2022	The phrase "for treatment of asthma" added to "Initiate therapy with another biologic" (Section 1.1, Section 4.2 and Section 4.2.1.2).	Yes, CSP 3.0	To clarify that the intercurrent event is related to the initiation of other biologic for treatment of asthma.
Derivation of primary or secondary endpoints	1-Dec-2022	Wording of the derivation of time at risk updated to highlight the need of subtracting time of asthma exacerbations and 7 days following an exacerbation (Section 4.2.2.2).	N/A	To provide clarification of time at risk derivation.
Derivation of primary or secondary endpoints	9-Nov-2023	Corrected time at risk derivation and combined into one step (Section 4.2.2.2)	N/A	To correct the derivation details for time at risk.
Population definition	20-May-2022	Participants assigned to Currently or historically elevated EOS population have to be dosed with at least dose of tezepelumab (Section 3.2.3).	N/A	To provide clarification of definition of Currently or historically elevated EOS population.

General study level definitions	9-Nov-2023	"Visit 9 (Week 28)" removed from the planned treatment definition and details provided which data should be included in the primary database lock at Week 28. (Section 3.3.1.1)	N/A	To clarify the definition of planned treatment period and how it should be handled at the time of primary database lock.
General study level definitions	9-Nov-2023	Updated general baseline definition to emphasize that for efficacy variables baseline is the last assessment at or prior to the date of first dose of IP administration, while for safety variables time of the first dose of IP administration is additionally considered. (Section 3.3.1.2)	N/A	To provide clarity on the time of baseline assessment and time of first dose of IP administration in the baseline definition.
Data presentation	11-Apr-2022	Visit window (Section 3.3.2) for Week 64 provided.	N/A	To provide missing information.
Data presentation	20-May-2022	Information how to classify countries into regions has been provided (Section 4.1.1.1).	N/A	To provide details of regions' definition.
Data presentation	20-May-2022	Participants' recruitment, as well as disposition and disruption due to global/country situation summary tables are presented based on Full analysis set, and not on All participants set (Section 4.1.1.2).	N/A	To clarify analysis set used in selected summary tables.
Data presentation	20-May-2022	Added information that participants' disposition is also presented graphically (Section 4.1.1.2).	N/A	To clarify the participants' disposition should also be presented on the graph often used in external materials (manuscripts, posters, etc.).
Data presentation	20-May-2022	Reference added to CSP Appendix I showing derivation of medium/high ICS group based on total daily ICS dose (Section 4.1.8.2).	Yes, CSP v2.0	To give details of derivation of medium/high ICS group.
Data presentation	20-May-2022	Shift tables have been added showing the daily OCS dose at baseline vs. the final OCS dose at Week 28, and the final OCS dose at	N/A	Analysis added to support the interpretation of the primary objective.

		Week 28 vs. the final OCS dose at Week 52 (Section 4.2.1.4).		
Data presentation	20-May-2022	The relation between the percent change from baseline in daily OCS dose at Week 28 (Week 52) and continuous baseline biomarkers (EOS, FeNO, total IgE) is presented graphically using nonparametric approach (Section 4.2.7.4).	N/A	To better explore the relation between percent change from bassline baseline in daily OCS dose and biomarkers level at baseline.
Data presentation	20-May-2022	Table presenting cumulative SCS dose over time added (Section 4.2.21.4).	N/A	Analysis added to support the interpretation of the endpoint of mean daily exposure of systemic corticosteroids.
Data presentation	20-May-2022	Specify that the mean cumulative SCS dose (mg) is presented on the graph with ± 1 standard error of the mean (Section 4.2.21.4).	N/A	To provide clarification on visual representation of the analysis results.
Data presentation	20-May-2022	The summary of number of dosing occasions added (Section 4.6.1.2).	N/A	To be aligned with data presentation across tezepelumab studies.
Data presentation	20-May-2022	AESIs are not presented on the overall AE summary tables. Information about intensity of AEs is listed and not summarised in the summary table (Section 4.6.2.2).	N/A	To be aligned with data presentation across tezepelumab studies.
Data presentation	1-Dec-2022	Details added of how the study population data is presented for Interim Analysis (Sections: 4.1.1.2, 4.1.4.2, 4.1.5.2, and 4.1.8.2).	N/A	To describe presentation of study population for the interim analysis.
Data presentation	1-Dec-2022	Additional sections regarding Interim Analysis added specifying derivation and presentation of efficacy endpoints (Sections 4.2.1.8 – 4.2.21.7).	N/A	To describe presentation of primary and secondary endpoints for the interim analysis.
Data presentation	1-Dec-2022	Clarification added that descriptive statistics for continuous secondary and exploratory endpoints are provided for both absolute	N/A	To clarify the presentation of continuous endpoints.

		values and changes from baseline (Sections: $4.2.8.4 - 4.2.21.7$).		
Data presentation	1-Dec-2022	Adjusted incidence rate definition added to the AE Section 4.6.2.1. Description of AEs presentation updated in Section 4.6.2.2. In addition, details regarding presentation of AEs for Interim Analysis provided in Section 4.6.2.2.	N/A	To clarify the presentation of AEs.
Data presentation	1-Dec-2022	The presentation of clinically important abnormalities of laboratory data (blood samples) updated from summary table to listing (Section 4.6.3.2).		To clarify the presentation of laboratory data.
Data presentation	9-Nov-2023	Added three additional categories to the disposition summary: participants who completed 28 weeks of treatment, participants who discontinued treatment at or prior to Week 28 (and reasons), and participants who withdrew from study at or prior to Week 28 (including reasons). (Section 4.1.1.2)	N/A	To improve clarity for the primary analysis at Week 28.
Data presentation	9-Nov-2023	Additional subgroups added to align with CSR requirements. (Section 4.2.1.7)	N/A	To align with CSR requirements.
Data presentation	9-Nov-2023	Added clarification on the minimal subgroup size required to conduct the model-based analysis i.e., the subgroup has to consist of at least 10 participants to be included in the model. (Section 4.2.1.7)	N/A	To provide clarity on small subgroups handling in the statistical models.
Data presentation	9-Nov-2023	Added definition, derivation and presentation details for participants requiring repeated morning cortisol testing for whom ACTH test is not available. (Section 4.2.14)	N/A	To provide information regarding the two steps for Adrenal Insufficiency testing (for details see CSP Appendix M).
Data presentation	9-Nov-2023	Removed listings of pregnancy test results and clarified that the analysis of positive results is	N/A	To align with Tezepelumab program reporting.

STATISTICAL ANALYSIS PLAN D5180C00037 – ed. 5.0

		not within the scope of this SAP. (Sections 4.6.4.2 and 4.6.5.2)		
Other	20-May-2022	A statement "mixed model for repeated measures (MMRM)" was replaced with "model for repeated measures" (Section 4.2.7.4).	Yes, CSP v2.0	To highlight that no RANDOM statement is used in the model specification.
Other	1-Dec-2022	Change from baseline in AIRQ TM and proportions of AIRQ TM responders at Week 28 have been deleted from exploratory endpoints (Section 1.1).	Yes, CSP v3.0	To align with CSP v3.0
Other	1-Dec-2022	Asthma exacerbation definition has been updated (Section 1.1, Section 1.2).	Yes, CSP v3.0	To align with CSP v3.0 definition.
Other	1-Dec-2022	Study design description updated (Section 1.2), including information about alternative method to ACTH stimulation test.	Yes, CSP v3.0	To align with CSP v3.0
Other	1-Dec-2022	Section 2 updated to remove changes which have been incorporated in revised CSP since SAP v3.0.	Yes, CSP v3.0	Following revision to CSP v3.0
Other	1-Dec-2022	Interim analysis (IA) has been added (Section 3.1, Section 5). Statement added that IA does not impact the sample size of the study (Section 1.3).	Yes, CSP v3.0	To align with CSP v3.0

